### 1.2 DRUG PROFILE

BI 1467335 is a small molecule AOC3 inhibitor that exhibits both anti-inflammatory and anti-fibrotic characteristics in various animal models. AOC3 is a membrane bound adhesion protein that facilitates the binding of leukocytes to endothelial cells and the subsequent

transmigration to sites of inflammation. The target indication of the compound will be NASH.

For a more detailed description of the BI 1467335 profile please refer to the current Investigator's Brochure (IB) [[c04751792](#)].

### Clinical experience

The clinical part of a phase I study [[c08854973](#)] just recently finished. This study investigated safety, tolerability, PK and PD of multiple doses

## 2. RATIONALE, OBJECTIVES, AND BENEFIT - RISK ASSESSMENT

### 2.1 RATIONALE FOR PERFORMING THE TRIAL

This trial is intended to examine the metabolism in humans, the mass-balance of excretion, plasma and urinary concentrations of BI 1467335

Major tasks involve the structure elucidation of metabolites as well as the [C]-radioactivity in blood cells, plasma, urine and faeces. This study will also help to determine the metabolic pathways following oral administration of [C]BI 1467335 in healthy volunteers.

The data are necessary for in-depth understanding of the pharmacokinetics of BI 1467335 including quantitative determination of elimination pathways and drug metabolites and are required for submission to regulatory authorities.

### 2.2 TRIAL OBJECTIVES

The main objective of this trial is to investigate the basic pharmacokinetics of BI 1467335, its metabolites, [C]-radioactivity, including mass balance, excretion pathways and metabolism following a single oral dose of 10 mg [C]BI 1467335 on Day 1 or on Day 28 during multiple dose treatment (Day 1 to Day 27 then Days 29 to last day of treatment) as determined by radioactivity collection with q.d. administration of non-labelled 10 mg BI 1467335 given to healthy male volunteers.

Primary objective is:

- To assess the mass balance recovery from excreta (urine and faeces) of [C]BI 1467335

Secondary objective is:

- To assess the  $C_{max}$  and  $AUC_{0-tz}$  for total radioactivity after single dose and after repeated doses and  $C_{max}$  and  $AUC_{0-tz}$  of BI 1467335 in plasma after single dose.
- To assess the  $C_{max,ss}$  and  $AUC_{0-\tau}$  for BI 1467335 in plasma after repeated doses.

A description of the endpoints to be determined, and the observations along with specific information as how to collect the data for that information, is provided in [Section 5](#).

### 2.3 BENEFIT - RISK ASSESSMENT

Participation in this study is without any (therapeutic) benefit for healthy subjects. Their participation in the study, however, is of major importance to the development of the compound. The subjects are exposed to the risks of the study procedures and the risks related to the exposure to the trial medication.

#### Procedure-related risks

The use of an indwelling venous catheter for the purpose of blood sampling may be accompanied by mild bruising and also, in rare cases, by transient inflammation of the wall of the vein. In addition, in rare cases a nerve might be injured while inserting the venous catheter, potentially resulting in paresthesia, reduced sensibility, and/or pain for an indefinite period. The same risks apply to veinipuncture for blood sampling.

The total volume of blood withdrawn during the entire study per subject will not exceed the volume of a normal blood donation (500 mL). No health-related risk to healthy subjects is expected from this blood withdrawal.

#### Drug-related risks and safety measures

##### *On target effects*

BI 1467335 could cause on-target toxicity as its anti-inflammatory effects may reduce the immune response and thus worsen infections. However, a deleterious effect relating to a reduction in leukocyte or lymphocyte migration was not seen in any of the preclinical models. This also true for two completed phase I studies in healthy male and female subjects

Nonetheless, clinical and laboratory signs of reduced immune response will be monitored throughout the study.

### *Drug-induced liver injury (DILI)*

Although rare, a potential for drug-induced liver injury (DILI) is under constant surveillance by sponsors and regulators. Therefore, this study requires timely detection, evaluation, and follow-up of alterations in selected liver laboratory parameters to ensure subjects' safety.

### *Administration of C-marked BI 1467335*

[C]BI 1467335 is labelled with the isotope [C] which is necessary for the purposes of this mass balance trial. Therefore, subjects will be exposed to ionizing radiation. The effective dose that each subject receives from one administration of 2 MBq is approximately 0.56 mSv (see [Appendix 10.1](#)). For biomedical investigations in small groups of healthy volunteers, an effective dose  $\leq 1.0$  mSv is considered acceptable.

### Summary of benefit-risk assessment

In a previous trial in healthy subjects, multiple oral doses of BI 1467335 administered once daily over 28 days were safe and well-tolerated. In the current trial, either single or multiple oral doses of 10 mg of BI 1467335 will be administered to healthy male volunteers. Each participating subject will receive only one radioactive dose.

The trial design is optimized to collect as much relevant information as possible on the pharmacokinetics of BI 1467335 without exposing participating volunteers to undue risk. However, there is always the potential of serious adverse events (SAEs) occurring with intake of trial medication. Risks to subjects will be minimized and addressed by eligibility criteria, safety laboratory examinations, ECG and vital sign measurements, in-house observation periods and verbal communication concerning AEs.

If the investigator should have any clinical concern, the safety of the subjects will be of paramount importance. The investigator has the discretion to remove subjects from the study should there be any safety concerns or if the subject's wellbeing is at jeopardy.

The risk associated with the expected maximal radiation burden falls in ICRP category IIa with minor level risk. This is considered to be acceptable.

The results of this trial are necessary for development of BI 1467335. Successful development of BI 1467335 is expected to provide a new valuable treatment for patients with NASH.

The risks of the participating volunteers are minimized and justified when compared to the potential benefits of this trial.

### 3. DESCRIPTION OF DESIGN AND TRIAL POPULATION

#### 3.1 OVERALL TRIAL DESIGN AND PLAN

The study will be performed as an open-label, single-arm and single- or multiple dose trial in healthy male subjects in order to investigate the basic pharmacokinetics of BI 1467335, and [C]-radioactivity, including mass balance following a single oral dose of [C]BI 1467335. For subjects assigned to the multiple dose treatment, the single oral dose of [C]BI 1467335 is dosed following multiple dosing of cold drug (Days 1-27 and 29-last dose given based on radioactive recovery, maximum Day 40).

The planned radioactive dose per subject is 2.0 MBq (54 µCi).

For the single dose part Day 1 is the day of [C] labelled drug administration. Subjects will stay in the study centre up to the morning of day 15 for the collection of samples of blood, urine, and faeces. Subjects will be readmitted to the study centre for 24 h collection intervals of urine and faeces on days 21, 28, 35, 42, and 49, if release criteria have not been met. Within 24 h before each of these once-weekly in-house collection intervals, subjects are to collect faeces at home. This 24 h interval home collection faeces will be used for analysis in case no defecation occurs in the subsequent 24 h in-house collection interval.

For the multiple dose part Day 28 is the day of [C] labelled drug administration. Non-labelled compound will be administered at site or at home during Day 1 to Day 27 and from Day 29 to Day 40 (dosing may be stopped before Day 40 if release criteria based on [C]-radioactivity have been reached for individual subjects, see below). From the evening of Day 27 to the morning of Day 43 subjects will remain in the study centre for the entire duration. Subjects will be released from the centre on Day 43. Subjects will then be readmitted to the study centre for 24 h collection intervals of urine and faeces on days 49, 56, 63, 70, and 77, if release criteria have not been met. Within 24 h before each of these once-weekly in-house collection intervals, subjects are to collect faeces at home. This 24 h interval home collection faeces will be used for analysis in case no defecation occurs in the subsequent 24 h in-house collection interval.

Single dose and multiple dose part will be conducted in different subjects. The study is planned to start with the multiple dose part, while the single dose part will be scheduled close to Day 28 of the multiple dose part.

For determination of whether release criteria have been reached for individual subjects, [C]-radioactivity will be measured in excreta (urine and faeces). The actual recovery results will be reported as a percentage of the administered dose.

If one of the following release criteria is true (i.e., release criteria have been met), 24 h collection intervals after day 15 (single dose) or Day 43 (multiple dose) will not be performed / will be stopped:

- Greater than or equal to 90% of the administered dose has been recovered in urine and faeces combined over the investigational period, *or*
- If <1% of the dose administered has been collected in urine and faeces within 2 separate, consecutive 24 h intervals, *and*
- Concentration of total radioactivity in plasma <5% of Cmax of total radioactivity in plasma

In the event that excretion release criteria are met after Day 15 (single dose) or Day 43 (multiple dose), but the mass balance recovery is less than 90%, subjects will still be asked to return to the clinic for 24 hour collection of urine and faeces on Days 21, 28, 35, 42, and 49 (single dose) or on Days 49, 56, 63, 70 and 77 (multiple dose) or until the recovery is deemed to be sufficient for mass balance purposes. If a subject is unable to attend one of these visits, they may be allowed to reschedule the visit if needed.”

Irrespective of whether release criteria have been met or not after collection interval Day 49-50 (single dose) or Day 77-78 (multiple dose), no further collections are planned.

An overview of all relevant trial activities is provided in the [Flow Chart](#). For visit schedule and details of trial procedures at selected visits, refer to [Sections 6.1](#) and [6.2](#), respectively.

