### 3.2 DISCUSSION OF TRIAL DESIGN, INCLUDING THE CHOICE OF CONTROL GROUP

This is a standard design for a [ $^{14}\text{C}$ ]-human study for investigation of absorption, distribution, metabolism, and excretion including determination of mass balance. Inclusion of a control groups is not required for this investigation. Despite of rapid elimination of radioactivity in rat ADME trials ([Section 1.2](#)), it cannot be excluded that prolonged sampling is still necessary in humans. Therefore, following 14 days in-house excreta collection after radioactive dosing (Treatment Group 1 on Day 1, Treatment Group 2 on Day 28 following a preceding treatment of unlabeled compound from Day 1 to Day 27), subjects will return on a weekly basis for in-house 24 h collection intervals for up to 7 weeks after last dosing as long as release criteria are not met ([Section 3.1](#)).

Blinding is not necessary, because all subjects receive the same dose per treatment group.

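### Section 3.1 both ends and continues weekly collections for the same subject below 90% recovery, and early stop of unlabelled multiple-dose treatment has two different triggers

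*Protocol*

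**What the plan says.** **Collection stop.** Section 3.1 sets the rule with "If one of the following release criteria is true (i.e., release criteria have been met), 24 h collection intervals after day 15" (or Day 43 in the multiple-dose group); such collections are then not done, or end. There are two criteria. The first is recovery of at least 90% of the dose in urine and faeces. The second joins two parts by 'and': under 1% of the dose in two consecutive 24 h intervals, and "Concentration of total radioactivity in plasma <5% of" Cmax.

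The next paragraph begins "In the event that excretion release criteria are met after Day 15 (single dose) or Day 43 (multiple dose") and continues "but the mass balance recovery is less than 90%, subjects will still be asked to return to the clinic" on the same weekly days, "or until the recovery is deemed to be sufficient for mass balance purposes". It gives no figure for sufficiency and names no one to judge it.

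Elsewhere only the stop rule appears. Earlier in Section 3.1, single-dose subjects return "on days 21, 28, 35, 42, and 49, if release criteria have not been met", with a matching sentence for the multiple-dose group. Section 3.2 has returns "for up to 7 weeks after last dosing as long as release criteria are not met" and refers back to Section 3.1. Flow Chart footnotes 5 and 6 in both groups end collection when the Section 3.1 criteria are met.

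**Dosing stop, multiple-dose group.** Section 3.1 describes unlabelled dosing after the labelled dose as Days "29-last dose given based on radioactive recovery, maximum Day 40". Sections 3.1 and 4.1.4 and SAP 6.1 allow ('may') an earlier end once the release criteria are met, and state no first day. Flow Chart Group 2 footnote 15 says that treatment will stop, from Day 35, if plasma radioactivity is below 10 dpm/mL. It has no recovery or excreta condition. The mark for footnote 15 stands on the Day 36 to Day 40 dosing rows.

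**The concern.** The two paragraphs of Section 3.1 give opposite instructions to one kind of subject, and neither is given precedence. The stop rule sets the end of the period from which both primary endpoints, urinary and faecal recovery from 0 to the last quantifiable time point, are drawn. Subject-specific windows are intended (Section 5.5.1.1 expects 2 to 7 weeks), but subjects in the same state should be handled alike.

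For dosing, two triggers measured in different matrices govern the same decision. The number of unlabelled doses that a healthy volunteer takes after the labelled dose can then depend on which page the site reads. SAP 6.1 carries only one of the two triggers.

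**Working it through.** The plan gives no figure to reproduce here, so the check is of logic and of nominal times.

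**1. Which subjects fall under both instructions?** Let A = recovery of at least 90%, B = under 1% of dose in each of two consecutive 24 h intervals, C = plasma under 5% of Cmax. The stop rule is A or (B and C). The return paragraph needs A false and the excretion criteria met, read either as B and C or as B alone.

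| A | B | C | Stop rule | Return paragraph |
|---|---|---|---|---|
| yes | any | any | stop | does not apply |
| no | no | any | continue | does not apply |
| no | yes | no | continue | return, or does not apply |
| no | yes | yes | **stop** | **return** |

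Only the last row conflicts, and it does so under both readings. A subject who meets B alone has met no release criterion and simply continues.

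**2. How many collections?** Nominal Flow Chart times, window ±4 h. The multiple-dose labelled dose is at 648 h and is subtracted.

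| | Single dose | Multiple dose |
|---|---|---|
| Discharge (Day 15 / 43) | 336 h | 1008 − 648 = 360 h |
| First weekly collection ends (Day 22 / 50) | 509 h | 1181 − 648 = 533 h |
| Last weekly collection ends (Day 50 / 78) | 1181 h | 1853 − 648 = 1205 h |

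- Criterion met after Day 15/43, as the text literally says: one weekly collection has been done and up to 4 are in dispute. Span 1181 − 509 = 1205 − 533 = 672 h.
- Subjects who meet it by discharge also covered, as the listing of Days 21 and 49 for return suggests: up to 5. Span 1181 − 336 = 1205 − 360 = 845 h.

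**3. How much recovery?** With under 1% per 24 h interval and excretion not rising, 4 collections add under 4 × 1 = 4 points and 5 add under 5. A subject at 86% or less after the first weekly collection, or at 85% or less at discharge, therefore stays below 90% through every remaining visit.

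**4. Can the state arise?** Take the 80 h half-life of Appendix A2 and assume mono-exponential excretion with a recoverable share R of 80% to 89%.

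- Recovery at 336 h: R × (1 − 2^(−336/80)) = R × 0.946, or 76% to 84%.
- The two daily intervals ending at 312 h and 336 h: 1.24–1.38% and 1.01–1.12%, so B is not yet met.
- Day 21 collection (485–509 h): R × (2^(−485/80) − 2^(−509/80)), about 0.22–0.25%. Day 28 collection: about 0.05–0.06%.
- Plasma at 485 h: 2^(−485/80) = 1.5% of its initial value, so C is met.

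Under these assumptions the conflicting state appears in the weekly phase.

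**5. Dosing triggers side by side.**

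| | Sections 3.1, 4.1.4; SAP 6.1 | Flow Chart footnote 15 |
|---|---|---|
| Trigger | A, or B and C | plasma below 10 dpm/mL |
| Force | may | will |
| First day | none stated | Day 35 (row marks from Day 36) |

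The plasma limits coincide only if Cmax = 10 / 0.05 = 200 dpm/mL. The documents give no Cmax. Over an assumed 50 to 2000 dpm/mL, the limit of 10 dpm/mL is 20% to 0.5% of Cmax. Either trigger can be met without the other. At 90% recovery with plasma above 10 dpm/mL, only the first is met. With plasma below 10 dpm/mL, recovery below 90% and more than 1% a day still excreted, only footnote 15 is met; it then requires a stop for which the other passages give no ground. The rows marked 15 hold 40 − 36 + 1 = 5 doses.

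**6. SAP 7.8.2.** The laboratory shift table describes its time point as a fortnight after the last dose. Single dose: 15 − 1 = 14 days, correct. Multiple dose: 43 − 40 = 3 days for the full course, or 43 − 35 = 8 days if Day 36 is the first omitted dose.

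**The case against.** The strongest reply on collections is that the second paragraph is an exception. Its wording presupposes the stop rule and sets it aside for a named subgroup, so a site that puts the specific before the general has a workable rule, capped at Day 50 or Day 78. That reading is plausible. However, the text does not state it, the earlier sentences of Section 3.1 and Flow Chart footnotes 5 and 6 do not carry it, and the end point of the extra visits stays undefined.

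A reader might infer that, under the exception reading, the second criterion has no function below 90%. The documents do not support that: read literally, a subject who meets it by the Day 15 or Day 43 discharge falls under the stop rule alone.

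On dosing, 'may' and 'will' can coexist, and the start of the row marks at Day 36 has a ready explanation. The Day 35 sample is drawn at 816:00, the Day 35 dosing time, so its result can first affect Day 36. Both points stand, and they confine the clear conflict to the trigger. A reader might also infer that all twelve doses from Day 29 to Day 40 are open because no first day is stated. That would need the criteria met and known before the Day 29 dose at 672:00, when the first faeces interval is only closing; the second criterion needs two intervals, so 696:00 at the earliest.

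**Conclusion.** Both inconsistencies are in the current text and should be fixed.

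- **Collections.** One state, below 90% with both parts of the second criterion met in the weekly phase, carries both instructions. Up to 4 collections are in dispute, or 5 if subjects who qualify by discharge are covered. The effect on recovery is under 4 (5) points, counting collected material only and assuming excretion does not rise. The 672 h and 845 h are scheduling spans; the endpoints run to the last quantifiable time point and are analysed descriptively, so their exposure is limited.
- **Dosing.** The clear conflict is plasma below 10 dpm/mL with the Section 3.1 criteria unmet. About 5 doses (Days 36 to 40) then depend on the passage followed. No effect on the BI 1467335 plasma endpoints is shown: Flow Chart Group 2 footnote 2 ends that sampling 24 h after the Day 28 dose.
- **SAP 7.8.2.** A reader might infer that the laboratory analysis shifts with the stop rule. It does not, because the SAP fixes Day 43 whenever dosing ends. The description of Day 43 is a separate error, present even when dosing runs to Day 40.

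**What to change.** 1. Merge the two Section 3.1 paragraphs into one prespecified collection-stop rule. It should state which instruction takes precedence below 90%, say whether subjects who meet the second criterion by Day 15 or Day 43 are covered, and either put a figure on sufficient recovery or delete that clause. Align the earlier readmission sentences of Section 3.1. Section 3.2 and footnotes 5 and 6 then follow by reference.
2. Sections 3.1 and 4.1.4, SAP 6.1 and Flow Chart Group 2 footnote 15 with its row marks must be reconciled so that trigger, first day and force agree. No view is given here on which dosing rule is right.
3. Whatever the outcome of item 2, correct the SAP 7.8.2 description of Day 43 for the multiple-dose group.

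The cost is wording in the protocol and in two SAP sentences (6.1 and 7.8.2). No subjects are added, and no visits or samples beyond the maximum already planned.

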### 3.1.1 Administrative structure of the trial

The trial is sponsored by Boehringer Ingelheim (BI) Pharma GmbH & Co. KG, Germany.

BI has appointed a Trial Clinical Monitor, responsible for coordinating all required activities, in order to

- manage the trial in accordance with applicable regulations and internal SOPs,
- direct the clinical trial team in the preparation, conduct, and reporting of the trial.
- ensure appropriate training and information of local clinical monitors (CML), Clinical Research Associates (CRAs), and participating trial sites.

The non-labelled trial medication will be provided by  
BI Pharma GmbH & Co. KG

The radiolabelled trial medication will be provided by

The trial will be conducted at  
under the supervision of the Principal Investigator.

Safety laboratory tests will be performed by the local laboratory of the trial site (

The analyses of BI 1467335 concentrations in  
plasma, the identification in urine, plasma, and faeces will be

performed at  
& Co. KG

BI Pharma GmbH

Blood, plasma, urine, and faeces concentrations of [ $^{14}\text{C}$ ]-radioactivity will be determined at

On-site monitoring will be performed by BI or a contract research organisation appointed by BI.

Data management and statistical evaluation will be done by BI according to BI SOPs.

Tasks and functions assigned in order to organise, manage, and evaluate the trial are defined according to BI SOPs. A list of responsible persons and relevant local information can be found in the ISF.

### 3.2 DISCUSSION OF TRIAL DESIGN, INCLUDING THE CHOICE OF CONTROL GROUP

This is a standard design for a [ $^{14}\text{C}$ ]-human study for investigation of absorption, distribution, metabolism, and excretion including determination of mass balance. Inclusion of a control groups is not required for this investigation. Despite of rapid elimination of radioactivity in rat ADME trials ([Section 1.2](#)), it cannot be excluded that prolonged sampling is still necessary in humans. Therefore, following 14 days in-house excreta collection after radioactive dosing (Treatment Group 1 on Day 1, Treatment Group 2 on Day 28 following a preceding treatment of unlabeled compound from Day 1 to Day 27), subjects will return on a weekly basis for in-house 24 h collection intervals for up to 7 weeks after last dosing as long as release criteria are not met ([Section 3.1](#)).

Blinding is not necessary, because all subjects receive the same dose per treatment group.

### 3.3 SELECTION OF TRIAL POPULATION

It is planned that 16 healthy male subjects will enter the study. They will be recruited from the volunteers' pool of the trial site or, if necessary, via advertisement.

The current trial is designed to investigate the basic pharmacokinetics of BI 1467335 including absorption, metabolism, and elimination and quantitative determination of excretion by mass balance.

Healthy male subjects are an ideal population for the objectives of this trial, since they provide relatively stable physiological, biochemical and hormonal conditions, i.e. the absence of disease-related variations and relevant concomitant medications.

A log of all subjects enrolled into the trial (i.e. having given informed consent) will be maintained in the ISF at the investigational site irrespective of whether they were given investigational drug or not.

